9.3.2. Evaluation of Selected Biomarker

Biomarker N-terminal (NT)-pro hormone brain natriuretic peptide (NT-pro-BNP) and changes from baseline at 4 and 8 hours after TPIP administration in single-dose inpatient treatment period will be summarized by dose group (if applicable) for the biomarker population. In a by-participant listing all observed time points together with their changes at 4 and 8 hours after TPIP administration will be listed.

A separate summary (if applicable) and listing will be provided for biomarker analysis set of EUT.

9.3.3. Evaluation of Changes in Selected Laboratory Parameter

The analysis of relevant changes in selected laboratory parameter will be described in Section 10.4.

9.3.4. Evaluation of Pharmacokinetics of Treprostinil Palmitil

The analysis of TP plasma PK parameter of C_{max} , t_{max} , AUC_{t1-t2} , AUC_{0-inf} , $t_{1/2}$, CL/F and Vd/F will be described in Section 11.

9.3.5. Evaluation of Respiratory Gas Exchange

Respiratory gas exchange parameter of minute ventilation, VCO₂, ETCO₂, SpO₂ (from respiratory gas exchange), oxygen pulse, oxygen consumption, heart rate, minute ventilation-CO₂ production ratio (VE/VCO₂) and its changes over 24 hours after TPIP administration in single-dose inpatient treatment period will be summarized by dose group (if applicable) and presented in a by-participant listing for the safety population.

9.3.6. Evaluation of TPIP on Parameters of Right Ventricular Function

Observed values of LVEF, TVR maximum velocity, TAPSE, and end diastolic right ventricular volume (indexed to BSA) and their changes from baseline at 2 to 8 hours after TPIP administration in single-dose inpatient treatment period will be summarized by dose group (if applicable) and presented in a by-participant listing for the safety population.

9.3.7. Evaluation of TPIP on Pulmonary Vasculature and Blood Flow Parameters

Pulmonary vasculature and blood flow parameters observed by a pulmonary CT scan for total blood volume, blood volume in vessels < 5mm² and their changes from baseline at 4 to 8 hours after TPIP administration in single-dose inpatient treatment period will be summarized by dose group (if applicable) and presented in a by-participant listing for the safety population.

9.3.8. Evaluation of TPIP on Exercise Capacity (6MWD), Extended Use Treatment Only

Observed values for 6MWD and the change in 6MWD from Baseline EUT to EUT Week 16 will be summarized by dose group (if applicable) for the safety population. A by-participant listing, using the same analysis population, will present the observed

values of single-dose inpatient treatment period and all observed values and its changes of EUT.

10. SAFETY

Unless otherwise stated, the safety population will be used for summaries and listings of safety variables.

10.1. Exposure to Study Drug and Compliance

As there is only one study drug administration in single-dose inpatient treatment period under direct observation of site personnel, an administration of study drug as planned will be assumed for this period.

The total exposure to study drug in EUT period will be calculated. The duration of EUT period will be calculated as described in Section 7.3.1. The start date duration of exposure in EUT will be the date of first dispensed study drug in EUT, the end date of EUT for duration of exposure will be the date of last study drug returned in EUT or the date of discontinuation of EUT (whatever occurs first). Compliance to intake of study drug will not be calculated and listed.

The exposure will be presented in a by-participant listing (study drug dosing date/time, date/time of discharge from hospital in single-dose inpatient treatment period, length of EUT period, total dose in EUT period) for the safety population.

10.2. Adverse Events

An AE is defined as any untoward medical occurrence associated with the use of a drug in humans, whether or not considered drug related. All AEs will be captured on the eCRF. The AE verbatim descriptions (investigator terms from the eCRF) will be classified into standardized medical terminology using MedDRA. AEs will be coded to primary SOC and PT using MedDRA, Version 25.0 or higher.

TEAEs are those AEs that occurred on or after the date/time of first study drug dosing and up to (and including) Study Day 30 follow-up visit or Study Day 30 follow-up of EUT for participants attending the EUT.

Where AE start dates are missing or partially missing, AEs will be assumed to be treatment-emergent, except if the partial start dates or the AE end date indicate that the AE started before the study drug dosing (see

Table 2).

Table 2: TEAE Assignment in Case of Missing AE Start Date Elements

Missing elements of AE start	Rule	
Regardless of any missing information for AE start: AE end date < first study drug dosing date non-		
Otherwise (i.e., if AE end date ≥ first study drug dosing date)		
- all		TEAE
- day and month	AE start year ≥ first study drug dosing year	TEAE
	AE start year < first study drug dosing year	non-TEAE
- day	AE start month / year ≥ first study drug dosing month / year	TEAE
	AE start month / year < first study drug dosing month / year	non-TEAE

Duration of AEs will be calculated in days (see Section 7.3.1). If date of onset or end date of event is not complete, duration will be set to missing.

An AE overview table for overall treatment group (if applicable also by dose group) will include number and percentage of participants and number of events with:

- AE;
- TEAE;
- Maximum severity of TEAE by participant;
- Treatment-related TEAE:
- Serious TEAE;
- Treatment-related Serious TEAE;
- TEAE leading to withdrawal of study drug, based on end of treatment eCRF;
- TEAE leading to withdrawal from study, based on end of study eCRF;
- TEAE resulting in death;
- AE related to COVID-19:
- TEAE related to COVID-19.

The overview table will be given for the whole study period, single-dose inpatient treatment period and EUT. The start of EUT will be the date of EUT Day 1.

A frequency table for overall treatment group (if applicable also by dose group) displaying TEAEs by SOC and PT will be provided. The summary will be ordered by descending number of participants with that SOC, the same is PT within each SOC. If more than one SOC is affected by the same number of participants, those SOC will be ordered alphabetically, the same is for PTs with the same SOC. The summary table will be given for the whole study period, single-dose inpatient treatment period and EUT.

All AEs. The listing will include all data collected for AEs, including a flag indicating treatment-emergency, onset day in relation to study drug dosing, duration of AE, and assignment of AE to single-dose inpatient treatment period or EUT.

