3. STUDY OBJECTIVES AND ENDPOINTS

3.1. Primary Objective and Endpoints

Objective	Endpoint
1. To evaluate the safety and tolerability of single doses of dry powder for inhalation formulation of treprostinil palmitil (TPIP) in participants with pulmonary arterial hypertension (PAH)	Frequency of treatment-emergent adverse events (TEAEs)

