3.4. Exploratory Objectives and Endpoints for the Optional Extended Use Treatment Period

Objective	Endpoint
To evaluate the safety and tolerability of TPIP in participants with PAH	Frequency of TEAEs during extended use treatment (EUT)
To assess the effect of TPIP on exercise capacity	Change from Baseline in 6MWD distance at EUT Baseline to EUT Week 16

6MWD = 6-minute walk distance

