7.2.2. Missing Start and Stop Dates for Adverse Events

The rules to categorize AEs to 'TEAE' or 'non-TEAE' are described in Section 10.2. Missing or partially missing start or stop dates will be not imputed.

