9. SAFETY AND EFFICACY

9.1. Primary Endpoint

The analysis of primary endpoint in terms of frequency of TEAEs will be described in Sections 10.2 to 10.3 of this SAP.

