10.6. Physical Examination

Any abnormalities noticed by investigator during the physical examination at screening will be recorded in the medical history, or as an AE if occurred or worsens after ICF was signed.

Dates of physical examination will not be listed.

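### The TEAE definition in SAP Section 10.2 goes by onset alone, so an AE with a known pre-dose start that worsens after TPIP under the same record is flagged non-TEAE

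*SAP*

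**What the plan says.** Section 3.1 names the frequency of TEAEs as the only primary endpoint. Section 9.1 passes its analysis on: "The analysis of primary endpoint in terms of frequency of TEAEs will be described in Sections 10.2 to 10.3 of this SAP". Section 7.2.2 does the same for classification: "The rules to categorize AEs to 'TEAE' or 'non-TEAE' are described in Section 10.2". Section 10.2 is therefore the controlling text.

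That section sets the lower bound: "TEAEs are those AEs that occurred on or after the date/time of first study drug dosing". The upper bound is the Day 30 follow-up, or the Day 30 follow-up of the EUT for those who enter it. Missing or partial start dates default to treatment-emergent, "except if the partial start dates or the AE end date indicate that the AE started before the study drug dosing". Table 2 puts this into rules. For example, when only the day is missing, an event is non-TEAE if "AE start month / year < first study drug dosing month / year".

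The only mention of worsening in the SAP is in Section 10.6. An abnormality seen at the screening physical examination goes into medical history, "or as an AE if occurred or worsens after ICF was signed".

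Section 3.4 makes TEAE frequency during the EUT an exploratory endpoint. The AE listing in Section 10.2 is to carry a treatment-emergent flag, the onset day and an assignment to the single-dose period or the EUT.

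**The concern.** A participant can have an AE before dosing. Section 4.1 allows up to 30 days of screening, and Section 10.2 plans separate overview rows for AEs and TEAEs, which only makes sense if some AEs are not treatment-emergent. Section 4.1 also warns that patients with PAH can become unstable quickly, so worsening of an event already present at dosing is foreseeable.

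Worsening after the drug is a tolerability signal. A definition that looks only at when the event began cannot register it. The loss carries through: maximum severity, treatment-related, serious, withdrawal and fatal TEAE rows, and the table by system organ class and preferred term, all start from the same flag.

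**Working it through.** There is no plan figure to reproduce. The sample size is not based on power (Section 4.3), and the point concerns a definition. The check sets the rules side by side and runs cases through them.

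**Step 1: does occurrence mean onset?** The lower bound speaks of AEs that occurred after dosing, which could be read loosely. The missing-date sentence settles it: the exception is "except if the partial start dates or the AE end date indicate that the AE started before the study drug dosing", so the test is when the AE started. Each rule in Table 2 compares a start or end date with the dosing date. None looks at severity or seriousness.

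**Step 2: does Section 10.6 supply the missing clause?** No. It is a recording rule, it covers only screening physical examination findings, and it is anchored to consent rather than to dosing.

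**Step 3: cases.**

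| Case | Classification under the SAP |
|---|---|
| (a) Complete start date between consent and dosing; worsens after TPIP; one record | Non-TEAE |
| (b) As (a), but the worsening is entered as a new record with a post-dose start | New record is a TEAE; the SAP does not say whether this is done |
| (c) Screening examination finding in medical history; worsens after dosing | AE under Section 10.6; TEAE if its start is dated at the worsening |
| (d) Ongoing at dosing; start wholly missing, or only the dosing year known, or only the dosing month and year known | TEAE under Table 2, whether or not it worsened |
| (e) Ongoing at dosing; day missing; known month before the dosing month; worsens after TPIP; one record | Non-TEAE under Table 2 |
| (f) Starts after the single dose, within the window; worsens in the EUT | TEAE for the whole study; no stated rule for the EUT assignment |

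Cases (a) and (e) are the gap. Cases (a) and (d) together show an inconsistency: an ongoing event with an incomplete start date in the dosing month counts even if it never changed, while a fully dated event that becomes severe after dosing does not.

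**Step 4: what reaches the output?** Section 5.2 reports one treated participant, listings only and no summaries. The AE listing in Section 10.2 covers all AEs, and Section 10.3 lists every AE resulting in death regardless of the flag. A case (a) event would therefore still be visible. Only its treatment-emergent flag would be wrong.

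**The case against.** The strongest objection is that the recording of worsening is usually settled in the protocol or the eCRF instructions, neither of which is shown. If those require a new record at worsening, every case (a) becomes case (b) and the SAP rule works. Section 10.6, the one place where the SAP deals with worsening, treats it as an AE in its own right, which leans that way. This stands as a possibility. However, the SAP does not state or rely on such a convention. Section 2 says that the SAP prevails where it and the protocol differ, so a worsening clause in the protocol's own TEAE definition would not rescue the flag. Section 12 lists no change on this point.

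The objection also disposes of several stronger readings:

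- A reader might infer that a pre-dose event that worsens is never counted. Cases (b) to (d) contradict that.
- A reader might infer that the rule can only undercount. Case (d) shows that Table 2 can also count an event that began before dosing and never worsened.
- A reader might put a size on it: one missed participant is 1/1 = 100 percentage points with the one treated, or 1/10 = 10 to 1/6 = 16.7 points with the planned 10 to 6. Those figures describe no planned output, because no frequency will be tabulated. They also assume that the participant had no other TEAE.
- A reader might infer that an event worsening in the EUT is fixed to the single-dose period. The SAP promises a period assignment but states no rule for this case, and only an exploratory endpoint is affected.

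**Conclusion.** The point holds in a limited form. Section 10.2 classifies by onset alone, so an AE with a known pre-dose start that increases in severity or becomes serious after TPIP, kept as one record, is flagged non-TEAE for the only primary endpoint. This is a stated rule that gives the wrong class, not merely an absent detail.

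Its present size is small: the treatment-emergent flag in the listing of one participant, with the event itself still listed. Whether any flag actually changes depends on two things that the SAP does not give: whether the participant had an AE ongoing at dosing that later worsened, and whether the eCRF opens a new record at worsening. Had the planned study been completed and tabulated, the same rule would have fed every TEAE count.

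**What to change.** In Section 10.2, define a TEAE as either an AE with onset on or after first dosing, or an AE present before first dosing that increases in severity or becomes serious on or after first dosing, in both cases within the existing window. Let the second condition take precedence over the Table 2 rows that give non-TEAE because of an early start month or year. The row for events that ended before dosing can stay as it is.

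Alternatively, state that worsening is entered as a new AE record with its own start date, in line with Section 10.6. If the eCRF already works this way, saying so is enough and no flag changes. This is also the practical choice if the eCRF does not date changes in severity within a record, which the SAP does not show.

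Apply the same test at EUT Day 1 for the exploratory EUT endpoint, and state how an event that worsens across periods is assigned.

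The cost is a sentence of text and one extra condition in the flag. The downside is a possibly slightly higher TEAE count. With one participant, the effect can be checked by reading the AE listing for events ongoing at dosing.

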10.3. Deaths

A by-participant listing of all AEs resulting in death will be provided.

10.4. Clinical Laboratory Evaluation

Laboratory test results and their changes from baseline (for numerical outcomes, if applicable) for hematology, clinical chemistry, coagulation, and serology tests will be summarized by time point.

All laboratory results and changes from baseline will be presented in a by-participant listing.

Table 3: Protocol-Required Safety Laboratory Tests

Category	Laboratory Parameters
Hematology	Hemoglobin, erythrocytes, hematocrit, MCH, MCV, MCHC, leukocytes, differential blood count of neutrophils, eosinophils, basophils, monocytes, lymphocytes, and platelets
Clinical Chemistry	Sodium, chloride, potassium, CO ₂ , magnesium, calcium, glucose, phosphate, total bilirubin (with direct and indirect fractionation, if total bilirubin is elevated >2 ULN), alkaline phosphatase, LDH, AST, ALT, CPK, albumin, total protein, creatinine, urea-nitrogen, uric acid, and estimated glomerular filtration rate
Coagulation	Prothrombin time, PTT, INR
Serology	HIV antibody, HBsAg, hepatitis C virus antibody

ALT = alanine aminotransferase; AST = aspartate aminotransferase; CO₂ = carbon dioxide; CPK = creatine phosphokinase; hCG = human chorionic gonadotropin; HIV = human immunodeficiency virus; HBsAg = hepatitis B surface antigen; INR = international normalized ratio; LDH = lactate dehydrogenase; MCH = mean corpuscular hemoglobin; MCHC = mean corpuscular hemoglobin concentration; MCV = mean corpuscular volume; PTT = partial thromboplastin time; ULN = upper limit of normal

10.5. Vital Signs

Heart rate, respiratory rate, systolic and diastolic blood pressure, body temperature, mean arterial pressure, and oxygen saturation will be collected at protocol specified visits and time points in single-dose inpatient treatment period and EUT. Measured values together with changes from baseline will be summarized by descriptive statistics by time point and by dose group (if applicable) and presented in a by-participant listing.

A separate summary (if applicable) and listing will be provided for safety analysis set of EUT.

10.6. Physical Examination

Any abnormalities noticed by investigator during the physical examination at screening will be recorded in the medical history, or as an AE if occurred or worsens after ICF was signed.

Dates of physical examination will not be listed.

10.7. Electrocardiograms

The results of overall investigator 12-lead ECG interpretation will be summarized by time point and by dose group (if applicable) and presented in a by-participant listing.

10.8. Pregnancy

Pregnancy results will be listed for all participants with outcome.

11. PHARMACOKINETIC ANALYSIS

11.1. Pharmacokinetic Sample Analysis

PK samples will be analyzed using a validated liquid chromatography coupled with tandem mass spectrometry assay for TRE and TP in human plasma. Assay results and validation details will be provided in a separate bioanalytical report.

11.2. Pharmacokinetic Sampling

Blood samples for PK analysis of TRE and TP will be collected at pre-dose, 30min, 60min, 2, 4, 8, 24, and 48h after dosing with TPIP in single-dose inpatient treatment period.

For the PK sampling, a window of \pm 10min will be allowed for sample collection at 30min, 60min, at 2h a window of \pm 20min, at 4h a window of \pm 1h, at 8 and 24h a window of \pm 2h, and a window of \pm 4h will be allowed at 48h planned sampling time.

Samples that are collected outside these windows will be logged as protocol deviations, but it is anticipated that PK data will still be used for PK parameter derivation.

11.3. Below the Limit of Quantification Values / Missing Values

For PK parameter calculations, pre-dose below the limit of quantification (BLQ) data will be treated as zero. All post-dose values BLQ will be considered as "missing". For descriptive statistical summaries and graphing, BLQ data will be considered as zero.

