7. GENERAL STATISTICAL CONSIDERATIONS

Due to the limited number of participants in the study and planned dose escalation after each participant, the observed study data will be presented in by-participant listings. By-participant listings will comprise of all observed data, e.g., single-dose inpatient treatment period and EUT. For selected data points, summaries will be provided only for an overall group. If three or more participants have received the same dose of study drug, summary tables will be provided for those dose group(s).

All statistical analyses will be conducted using statistical analysis system SAS® Version 9.4 or higher (SAS Institute, Cary, NC).

Descriptive statistics for continuous variables include n, mean, standard deviation (SD), median, minimum, maximum, 1st quartile and 3rd quartile (if required). Summaries of continuous variables that have some values recorded using approximate values (e.g., < or >) will use the numeric part of the value in calculations. Listings will present the data in its original format.

Categorical variables will be tabulated by counts and by percentage of participants in corresponding categories. Footnotes will specify the basis for the percentages.

Data from unscheduled visits will not be used in summaries, except for the derivation of baseline.

Listings corresponding to all summaries in this section will be provided. Listings will show data from scheduled and unscheduled visits.

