11.5. Pharmacokinetic Statistical Analysis

Plasma concentrations of TRE and TP will be presented in a by-participant listing for the PK analysis set.

Plasma concentration versus time profiles based on actual sampling times for each participant will be presented graphically at linear and log scale.

PK parameters for TRE and TP will be presented in a by-participant listing for the PK analysis set.

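### Setting every post-dose BLQ concentration to missing makes the AUC interpolate through early samples measured as BLQ; the effect is conditional and usually small, and log-scale plots need their own BLQ rule

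*SAP*

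**What the plan says.** SAP Section 11.3 gives three rules for BLQ concentrations.

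- Parameters, pre-dose: "For PK parameter calculations, pre-dose below the limit of quantification (BLQ) data will be treated as zero".
- Parameters, post-dose: "All post-dose values BLQ will be considered as" missing. The rule covers all post-dose values and does not separate those before the first quantifiable sample (leading), those between quantifiable samples (embedded) and those after the last one (trailing).
- Summaries and plots: "For descriptive statistical summaries and graphing, BLQ data will be considered as zero".

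Section 11.2 has samples "collected at pre-dose, 30min, 60min, 2, 4, 8, 24, and 48h after dosing with TPIP". Section 11.4 computes AUC0-t by linear-up/log-down, so the rising limb uses linear trapezoids, and defines CL/F as dose over AUC0-inf. Section 11.5 lists the parameters by participant and requires concentration profiles that "for each participant will be presented graphically at linear and log scale". Section 5.2 records that the study was terminated with one participant treated, that the data will only be listed, and that the later sections describe what had been planned.

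**The concern.** A leading BLQ result is information: at that time the concentration was below the assay limit. Setting it to missing discards that information. Because pre-dose is fixed at zero, the first trapezoid then runs from dosing to the first quantifiable sample. The area credited to that interval may imply concentrations that the assay would have detected.

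At stake are AUC0-t and AUC0-inf (secondary for treprostinil, exploratory for treprostinil palmitil) and, through AUC0-inf, CL/F and Vd/F. Cmax, tmax and the half-life are not affected. A rule that treated the leading samples separately would avoid the problem at almost no cost.

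A second, smaller matter is that zero has no position on a logarithmic axis. The graphing rule of Section 11.3 therefore gives the programmer no usable instruction for half of the plots that Section 11.5 requires. A single BLQ pre-dose sample is enough to raise this.

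**Working it through.** The SAP gives no AUC value, assay limit (LLOQ) or expected profile, so there is no planned figure to reproduce. The sampling times (0, 0.5, 1, 2, 4, 8, 24, 48 h) and the AUC method come from Sections 11.2 and 11.4. Profile shapes and LLOQ values below are assumptions.

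**1. Exact excess.** Let the first quantifiable value be C at time t(k), with every earlier post-dose sample BLQ.

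- Section 11.3 rule (missing): first segment = C × t(k)/2.
- Leading BLQ set to zero: first segment = C × [t(k) − t(k−1)]/2.
- Difference = C × t(k−1)/2.

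| First quantifiable sample | Last BLQ sample | Missing rule | Zero rule | Excess |
|---|---|---|---|---|
| 1 h | 0.5 h | 0.5 C | 0.25 C | 0.25 C |
| 2 h | 1 h | 1.0 C | 0.5 C | 0.5 C |
| 4 h | 2 h | 2.0 C | 1.0 C | 1.0 C |
| 8 h | 4 h | 4.0 C | 2.0 C | 2.0 C |

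If the 30-minute sample is quantifiable, no leading post-dose BLQ exists and the excess is zero.

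**2. When the line contradicts the assay.** The interpolated value at t(k−1) is C × t(k−1)/t(k). For each row above, t(k−1)/t(k) = 1/2, so the implied value is C/2. It exceeds the LLOQ, and so contradicts the BLQ result, whenever C is more than 2 × LLOQ. With C = 4 × LLOQ, for example, the line implies 2 × LLOQ at a sample measured as BLQ.

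**3. Size under one-compartment absorption profiles.** Assumptions: half-life 4 to 12 h, absorption rate 0.15 to 1.0 per h, lag 0 to 1 h, LLOQ 5% to 20% of Cmax. Where a leading BLQ arises, the missing rule gives an AUC0-t 0.1% to 8.2% above the zero rule. One example, with concentrations scaled to Cmax: half-life 8 h, rate 1.0 per h, lag 1 h, LLOQ 10% of Cmax. The first quantifiable sample is at 2 h. AUC0-t is 12.545 against 12.165; the difference is 0.380, and 0.380/12.165 = 3.1%.

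**4. Size under an extreme shape.** Assume that the first quantifiable value is the peak and is followed at once by mono-exponential decline to 48 h. Tail = C × (h/ln 2) × [1 − 2^(−(48 − t(k))/h)], with h the half-life.

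- h = 2 h, first value at 1 h: (0.5 + 2.885)/(0.25 + 2.885) = +8.0%.
- h = 2 h, first value at 2 h: (1.0 + 2.885)/(0.5 + 2.885) = +14.8%.
- h = 2 h, first value at 4 h: (2.0 + 2.885)/(1.0 + 2.885) = +25.7%.
- h = 12 h, the same three cases: +1.5%, +3.0% and +5.9%.

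**5. A sparse profile near the limit.** Assume LLOQ = 1 and concentrations 0.4, 0.6, 0.8, 1.3, 1.1 at 0.5, 1, 2, 4, 8 h, with later samples BLQ. The 4 to 8 h log-down segment is (1.3 − 1.1) × 4/ln(1.3/1.1) = 4.789.

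- Missing rule: 4 × 1.3/2 + 4.789 = 7.39.
- Zero rule: 2 × 1.3/2 + 4.789 = 6.09. The missing rule is 21% higher.
- Trapezoids on the uncensored concentrations: 0.10 + 0.25 + 0.70 + 2.10 + 4.789 = 7.94. The missing rule is 6.9% below this, and the zero rule is further below.

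Here C = 1.3 × LLOQ, so by step 2 the interpolated line does not contradict the assay.

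**6. Against the truth more generally.** In simulated profiles with lag-time or transit absorption (assumed shapes), the zero rule was closer to the true area of the early segment in 80% to 93% of cases. In the step 3 profiles, measured against the uncensored concentrations at the sampling times, the missing rule ranged from +8.2% (with an absorption lag) to −0.03% (no lag).

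**7. Knock-on to clearance.** CL/F = dose/AUC0-inf. When the terminal slope is estimable, AUC0-inf carries the same absolute excess as AUC0-t. An AUC0-inf that is 8.2% too high, for instance, lowers CL/F by 1 − 1/1.082 = 7.6%. Vd/F falls in the same proportion.

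**The case against.** **Zero is also an imputation.** Where early concentrations sit just under the limit, the missing rule can be nearer the truth, as step 5 shows. This stands. A reader might infer that Section 11.3 always inflates AUC, but the plan does not support that. The certain statement is only that AUC is higher than under leading-BLQ-as-zero.

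**The large percentages need special shapes.** The 15% and 26% figures require a 2 h half-life and a first quantifiable value that is already the peak. Slow release, the setting in which leading BLQ is most likely, tends to make C a small fraction of Cmax and so shrinks the excess. This also stands.

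**A leading BLQ may never occur.** Sampling starts 30 minutes after inhalation and the SAP gives no LLOQ. The frequency cannot be judged from the document.

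**Little is left to bias.** With one participant and listings only, there is no pooled estimate or dose-group mean. That limits the weight, but Section 11.5 still lists that participant's parameters, and no averaging can dilute an artefact in them.

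**The plot conflict is cosmetic.** No estimate uses the plot, and software will probably leave the zeros off the log axis anyway. Section 5.2 may even mean that no plots are produced, although it does not clearly withdraw individual profiles. The wording still needs correction.

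**Section 7.** A reader might infer a third treatment of the same datum, because Section 7 says that summaries of values recorded with a less-than sign "will use the numeric part of the value in calculations". That does not hold. The Section 7 rule covers summaries only, Section 11.3 is the specific rule for concentrations, and Section 11.5 plans no concentration summary.

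**Conclusion.** The point holds in a limited form and is minor in practice. The post-dose BLQ rule is reasonable for trailing values, because AUC0-t ends at the last quantifiable concentration. It is poorly chosen for leading values, where it replaces a measured BLQ result with a straight line that can lie above the assay limit.

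The effect relative to leading-BLQ-as-zero is exactly C × t(k−1)/2. That is mostly below about 8% of AUC under the assumed absorption profiles, and reaches 15% to 26% only in the sparse or short-half-life cases shown. It is nil without a leading post-dose BLQ. These percentages rest on assumed profiles and limits; the algebra does not. The direction relative to the true AUC is usually upward for the early segment but is not guaranteed. The reach is one participant's listed AUC, CL/F and Vd/F.

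The conflict between BLQ-as-zero for graphing and the log-scale profiles is real, but it changes no estimate.

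**What to change.** In Section 11.3, split the parameter rule: BLQ values from pre-dose up to the first quantifiable sample are set to zero, and embedded and trailing BLQ values remain missing. Limit the zero rule for graphing to linear-scale plots, and state that BLQ points are omitted from log-scale plots and footnoted.

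The cost is two sentences of SAP text and a standard setting in the noncompartmental software. If the parameters have already been derived, first check whether the treated participant had a BLQ result before the first quantifiable sample, for either analyte. If not, the parameters stand and only the wording changes. If so, rederive AUC, CL/F and Vd/F for that analyte and note the change in the study report.
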